Annex VI Summary of amendments to OneRIF Protocol version 3.0

- Throughout the protocol the NCT code is added and the protocol version number and date were adapted.
- On pages 2, 3 and 5 [name] [name] is added as back-up of the ITM study coordinating investigator [name] [name].
- On pages 2, 3 and 5 [name] is added as back-up of the DF study coordinating investigator [name].
- On page 3 the list of CTU members involved in the study is updated.
- On page 8 the instructions on how to write the synopsis are deleted.
- On pages 16 and 17, section 3.1 primary endpoints, the outcome definitions are updated
- On page 17 the section 3.2 secondary endpoints is updated.
- At the top of page 23 a sentence is deleted.
- On pages 25 and 26 the sections of microscopy and DST and species identification are updated.
- On page 31 an interim statistical analysis is added.
- Reference 18 is updated on page 39.

## 1. Introduction

This Statistical Analysis Plan (SAP) provides a detailed and comprehensive description of the main, pre-planned analyses for the study "Optimization of the TB treatment regimen cascade", including the recently approved interim analysis. The purpose of this study is to compare a high-dose rifampicin standard TB regimen of 6 months duration with the standard TB regimen in respect to adverse treatment outcome (relapse, failure, death and default) and toxicity, in smear-positive pulmonary TB cases. The study conduct is described in the Protocol.

These planned analyses will be performed by the statistician(s) at the Clinical Trials Unit of the Institute of Tropical Medicine (Antwerp) in collaboration with the research consortium. The analysis results will be described in a statistical analysis report, to be used as the basis of the primary research publications. This document describes statistical methods for the primary and secondary objectives of the study as defined by protocol. Additional analyses may be performed but are not covered by the current analysis plan.

Analyses will be performed at three time-points.

1) Assessment of referral for rapid DST plus its outcome based on the auramine and/or FDA decline for the patients randomized in the intervention arm versus persisting fever, for the patients randomized in the control arm, 2 weeks after the first 500 enrolled patients (intervention + controls) reached two weeks follow-up. With this analysis we want to assess whether any of those can really be used as an early indicator of serious rifampicin resistance, and also assess the impact of improvement of staining techniques that were made after the first ITM monitoring visits. The results in terms of resistance missed / correctly suspected will be analysed based on the initial genetic rifampicin resistance data which will by that time also be available for part of these patients.

2) Assessment of drug toxicity and initial treatment response will be performed at the time the last recruited patient finishes treatment. The data will be compiled at 9 months after the end of recruitment to ensure all treatment related data, including 8 months of treatment for retreatment cases in the control arm, are available. This analysis will be primarily performed for the go/no-go decision and design considerations for a possible next study, such as a cluster-randomized trial. The decision on proceeding to the cluster randomized study will be based on the absence of excess toxicity, a trend toward a reduction of unfavourable outcomes (excluding relapse), possible favourable effects overcoming low-resistance mutations.

3) A final analysis of the study endpoints, including relapse, will be performed one year after end of treatment of the last enrolled patients, i.e. about 2.5 years after enrolment start.

This analysis plan will be finalized and approved before database lock of the first interim analysis data. Major changes in statistical methodology used for the main and pre-planned analyses from this SAP, will require detailed description and justification in the statistical analysis report. The final analysis datasets, programs, and outputs are archived following good clinical practice guidelines (ICH E9).

## **2. Study design and objectives**

### **2.1. Study design**

This study is an open-label randomised clinical trial. Consecutively diagnosed smear-positive pulmonary TB patients, which conform to all of the inclusion and none of the exclusion criteria and provide informed consent, will be randomized to the intervention or control arm.

The control arm will receive the standard pulmonary TB treatment regimens recommended by the International Union against Tuberculosis and Lung Disease (The Union). This consists of:

#### Treatment:

*New cases:* 2HRZE/4HR, i.e. 2 months of isoniazid, rifampicin, pyrazinamide and ethambutol intensive phase, followed by 4 months continuation phase isoniazid plus rifampicin) (Cat. 1 regimen, 6 months)

*Retreatment cases:* 2 months of SHRZE (S= streptomycin) followed by 1 month of HRZE and 5 months HRE (Cat. 2 regimen, 8 months)

Any patients with *MDR TB detected* at any time will be switched to 4KHPtoGCEZ/5GCEZ, i.e. 4 months of kanamycin, isoniazid, prothionamide, gatifloxacin high-dose, clofazimine, ethambutol and pyrazinamide, followed by 5 months of gatifloxacin high-dose, clofazimine, ethambutol and pyrazinamide (MDR regimen, 9 months)

#### Testing:

Monitoring by smear and rapid DST as per National TB Programme (NTP) indications:

- Smears for AFB [by Ziehl-Neelsen brightfield (ZN) or auramine fluorescence (FM) technique] at diagnosis, after 2, 5 and 6 months (Cat. 1) or after 3, 5 and 8 months (Cat. 2); repeat after month 3, respectively 4, if AFB were seen at month 2 or 3
- Vital staining fluorescein diacetate (FDA) smears for AFB to confirm a positive ZN or FM result during Cat. 1
- rapid DST if fever is still present after 2 weeks, or in case an AFB smear (auramine and/or FDA) is positive during Cat. 1, or from the 3rd month of Cat. 2 onwards. Rapid DST is performed also from any retreatment case (relapse, return after default and other previously treated for at least 1 month), and from previously untreated contacts of MDR-TB

Additionally, patients enrolled in the study (control as well as intervention arm) will be followed-up for relapse 12 months after the end of treatment by clinical examination, sputum smear and slow solid culture.

The intervention consists of the standard care as provided to the control arm with the following modifications:

#### Treatment:

*New cases:* Compared to standard regimen dosing of rifampicin is doubled, while standard dose isoniazid, pyrazinamide and ethambutol are maintained, i.e. 2 months of HRhZE followed by 4 months of HRh (6 months)

*Retreatment cases:* retreatment cases randomized to the intervention arm receive the same care as new cases in the same arm.

Any patients with *MDR TB detected* at any time will be switched to 4 months of KHPtoGCEZ followed by 5 months of GCEZ (MDR regimen)

#### Testing

In addition to standard monitoring (as described above for the control arm), patients in the intervention arm will have sputum tested by auramine and FDA smear after the first and again after the second week of intensive phase treatment. Management decisions will be made after 2 weeks of intensive phase, based on remaining numbers and decline of AFB on FDA staining, but not based on continuing fever. Those with min. 1 log decline in the number of AFB, or who are already negative, would continue the unaltered regimen. Those not meeting these criteria would be referred for rapid DST by slide DST and/or Xpert MTB/RIF, depending on ease of referral.

#### 2.2. Study objectives

An additional secondary objective has been added, compared to the objectives in the protocol.

#### *Primary objective:*

To compare a high-dose rifampicin standard TB regimen of 6 months duration with standard TB regimen with respect to adverse treatment outcome (relapse, failure, death and default) and toxicity, in TB cases (new or retreatment, pooled) not shown to have rifampicin resistance before one of the standard treatment outcomes applies.

*Secondary objectives:*

1. To assess whether the study regimen also cures low-level rifampicin resistant TB
2. To assess the effectiveness of FDA vital staining screening at two weeks of treatment for early switch of non-responding rifampicin resistant TB to MDR-TB treatment, versus clinical evaluation based on fever resolution.
3. To assess the negative predictive value of conversion at 2 weeks for relapse
4. To estimate the proportion of acquired rifampicin resistance among failures and relapses
5. To compare the predictive value of auramine with FDA staining at 2 weeks to predict unfavourable outcomes
6. To compare weight gain and fever resolution between the two regimens

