4.4 Randomization

Two randomization lists will be prepared at ITM prior to study start: one for new cases, one for retreatment cases. To ensure (approximate) treatment balance within study sites, the randomization list will be blocked. Treatment allocation will be concealed until the completion of the screening procedures and the final recruitment of the patient using sealed envelopes labelled with the randomization number and containing the treatment group allocation.

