5.3 Specific procedures and activities

- Screening visit:
 - o Clinical symptoms and signs of TB to select suspects for AFB-smear; refer to Medical Officer if not a suspect
 - o Spot sputum collected for AFB if responding to TB suspect criteria; request for a second early-morning sputum next day
 - If AFB positive and patient does not respond to MDR suspect criteria: proceed with V0 procedures (same day if possible)
 - If positive and patient responds to MDR suspect criteria (MDR contact or retreatment case): referral for DST, treatment depending on rapid result
 - MDR regimen if rifampicin resistant; not eligible for the study
 - if susceptible or no result: eligible, continue with V0
- Enrolment visit V0:
 - o Always clinical symptoms and signs, medical history, weight, temperature, patient information on standard TB treatment and DOT arrangements
 - Medical history: previous TB treatment; concomitant disease such as diabetes and HIV
 - o Signs and symptoms: check for vital signs, severe anemia, dyspnea, chest pain, suspect of TB complications: refer if severely ill or complications suspected. Responding to exclusion criteria: register as non-study and start standard TB treatment or refer (active liver disease, patients to be hospitalized...)
 - o No exclusion: explain study, ask informed consent
 - Refused: register as non-study and start standard TB treatment
 - Accepted: perform study specific procedures
 - Perform urinary pregnancy test for all women of childbearing age not aware that they are pregnant. If the test is positive, do not include in the study but register as non-study patient and start on standard TB treatment.
 - Pregnancy excluded: liver test, register as study patient and randomise to intervention or control arm
 - **Intervention only:** quantified auramine and FDA smears; start high-dose Cat. 1
 - Control arm: start Cat. 1 or Cat. 2 depending on history
- Visit after one week V1: **intervention patients only**
 - o Give treatment, record attendance
 - o Sputum for quantified AFB smears (auramine and FDA)
 - o Stop all drugs and refer in case of hepatitis suspicion (feeling sick, anorexia, vomiting, jaundice)
- Visit after two weeks V2: Intervention + control arm
 - o Clinical check, weight, temperature: improving signs and symptoms of TB?
 - o Give treatment, record attendance
 - o Liver test
 - o **Intervention arm only:** Sputum for quantified AFB smears (auramine and FDA), apply algorithm

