 - refer for rapid DST if indicated by algorithm; switch to MDR if rifampicin resistant
 - otherwise continue high-dose treatment
 - o **Control arm only:**

- refer for rapid DST if still fever (temperature $\geq 38^{\circ}\text{C}$); switch to MDR if rifampicin resistant
 - Enquire, register adverse effects. Stop all drugs and refer in case of hepatitis suspicion (feeling sick, anorexia, vomiting, jaundice)
- Visit after four weeks V3: intervention + control arm
 - Clinical check, weight, temperature: improved signs and symptoms of TB?
 - Give treatment, record attendance
 - Liver test
 - Enquire, register adverse effects. Stop all drugs and refer in case of hepatitis suspicion (feeling sick, anorexia, vomiting, jaundice)
- Visit after 2 months V4: intervention + control arm
 - Clinical check, weight, temperature: signs and symptoms of TB absent?
 - Give treatment, record attendance
 - Cat. 1: sputum smear for AFB
 - Refer for rapid DST if AFB-positive (auramine and FDA) and clinically poor evolution; switch to MDR treatment if rifampicin resistant
 - Liver test
 - Enquire, register adverse effects. Stop all drugs and refer in case of hepatitis suspicion (feeling sick, anorexia, vomiting, jaundice)
- Visit after 3 months V5: intervention + control arm
 - Clinical check, weight, temperature: signs and symptoms of TB absent?
 - Give treatment, record attendance
 - Sputum smear for AFB: all Cat. 2 and Cat. 1 patients positive at month 2
 - Refer for rapid DST if AFB-positive (auramine and FDA); switch to MDR treatment if rifampicin resistant
 - Enquire, register adverse effects. Stop all drugs and refer in case of hepatitis suspicion (feeling sick, anorexia, vomiting, jaundice)
- Visit after 4 months V6: intervention + control arm
 - Clinical check, weight, temperature: signs and symptoms of TB absent?
 - Give treatment, record attendance
 - Sputum smear for AFB: Cat. 2 positive at month 3 only
 - Refer for rapid DST if AFB-positive; switch to MDR treatment if rifampicin resistant
 - Enquire, register adverse effects. Stop all drugs and refer in case of hepatitis suspicion (feeling sick, anorexia, vomiting, jaundice)
- Visit after 5 months V7: intervention + control arm
 - Clinical check, weight, temperature: signs and symptoms of TB absent?
 - Give treatment, record attendance
 - Sputum smear for AFB: all patients
 - Declare failure if positive and refer for rapid DST if AFB-positive
 - Switch to MDR treatment if rifampicin resistant

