7.6. To compare weight gain and fever resolution between the two regimens

Weight gain between enrollment and end of treatment will be compared between the two regimens using the t-test or Wilcoxon rank sum test, as appropriate. Fever resolution after two weeks of treatment will be compared between the two regimens using the chi-squared or Fisher's exact test.

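### SAP 7.6 compares week-2 fever resolution by an unadjusted test with no effect estimate and no stated denominator; an adjusted odds ratio would use data already recorded in both arms

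*SAP*

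**What the plan says.** SAP 2.2 states: "An additional secondary objective has been added, compared to the objectives in the protocol". The addition is objective 6: "To compare weight gain and fever resolution between the two regimens". SAP 7.6 gives the whole fever method in one sentence: "Fever resolution after two weeks of treatment will be compared between the two regimens using the chi-squared or Fisher's exact test". It names no covariate, stratum, site, effect measure, confidence interval, fever cut-off or denominator. Because the objective is not in the protocol, the protocol cannot fill these gaps.

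The data are available. At enrolment, before randomisation, Protocol 5.3 requires "Always clinical symptoms and signs, medical history, weight, temperature". The week-2 visit, attended by both arms, records temperature again, and the schedule in Protocol 5.1 agrees. Protocol 4.4 prepares two randomisation lists, "one for new cases, one for retreatment cases". A cut-off of 38 °C appears in Protocol 5.1 and 5.3, but only as the control-arm trigger for rapid DST.

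Elsewhere the SAP adjusts: the primary model (section 6) and the safety models (8.2.1 and 8.2.2) include hospital and stratum. Protocol 8.1 puts the emphasis on odds ratios with 95% CIs rather than on formal testing.

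**The concern.** Scheduled smears at weeks 1 and 2 are taken only in the intervention arm, so week-2 temperature is one of the few early response measures that allow a randomised comparison. SAP 7.6 uses it sparingly, in three ways.

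- **Enrolment temperature is left out.** It is a natural predictor of week-2 fever and is measured before randomisation.
- **The stratum is left out.** This departs from the SAP's own models. It also matters for interpretation: at week 2, retreatment controls are on a regimen containing streptomycin and new controls are not, while the intervention regimen is the same in both strata.
- **The result is only a p-value, on an undefined denominator.** Only a patient febrile at enrolment can resolve a fever. Two analysts could follow 7.6 faithfully and report different proportions.

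At stake are the precision and reproducibility of one secondary result. The validity of the trial is not in question.

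**Working it through.** **The plan's own figure.** There is none for fever. The plan's sample-size figure, 1421 per arm for 10% v 7%, concerns the primary endpoint. It reproduces as 1422 with the continuity correction (1356 without) and does not bear on this point.

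**Inputs.** From the documents: 500 per arm (Protocol 4.3), two strata, temperature at enrolment and week 2. Fever prevalence, temperature SD, the correlation ρ between the two temperatures, and the effect are all assumed.

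**Step 1: cost of a yes/no cut if the regimen shifts temperature generally.** With normal temperatures and a proportion p febrile at week 2, the share of information kept is φ(z_p)²/[p(1−p)]. For p = 0.10: z = 1.2816, φ = 0.1755, and 0.0308/0.09 = 0.34. For p = 2%, 5%, 10%, 20%, 30% and 50% the share is 12%, 22%, 34%, 49%, 58% and 64%. Against linear regression on enrolment temperature, multiply by (1−ρ²). With ρ from 0.3 to 0.7 this gives about 6% to 58%.

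**Step 2: simulated power (%), two-sided 5%, 1,500 runs per setting.** The columns are chi-square in all patients; chi-square only in those febrile at enrolment; logistic regression in all patients with enrolment temperature and stratum; and linear regression of week-2 temperature with the same covariates. Hospital was not simulated.

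*General shift of 0.125 °C, SD 0.7 °C:*

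| Febrile at enrolment / week 2 | ρ | Chi-square, all | Chi-square, febrile only | Logistic, all | Linear |
|---|---|---|---|---|---|
| 30% / 5% | 0.3 | 25.8 | 15.0 | 26.2 | 82.9 |
| 30% / 5% | 0.5 | 26.3 | 18.1 | 26.5 | 90.9 |
| 30% / 5% | 0.7 | 24.0 | 21.3 | 30.8 | 98.0 |
| 50% / 10% | 0.3 | 37.3 | 26.8 | 38.5 | 83.7 |
| 50% / 10% | 0.5 | 35.5 | 28.5 | 39.7 | 90.6 |
| 50% / 10% | 0.7 | 35.7 | 34.1 | 44.9 | 97.5 |
| 60% / 20% | 0.3 | 48.1 | 37.1 | 49.1 | 83.3 |
| 60% / 20% | 0.5 | 48.9 | 41.9 | 54.3 | 91.3 |
| 60% / 20% | 0.7 | 48.5 | 47.2 | 62.9 | 97.1 |

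*The regimen changes only whether a febrile patient stays febrile (10% retreatment):*

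| Febrile at enrolment | Stay febrile, control v intervention | Chi-square, all | Chi-square, febrile only | Logistic, all | Linear |
|---|---|---|---|---|---|
| 30% | 30% v 20% | 41.1 | 53.4 | 45.5 | 26.5 |
| 50% | 20% v 12% | 62.5 | 69.4 | 65.5 | 38.9 |
| 60% | 30% v 22% | 56.1 | 62.8 | 60.8 | 42.1 |

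**Step 3: reading the tables.**

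- Adjusted logistic regression is at or above the all-patient chi-square in all 12 settings. The gain runs from 0.2 points (26.5 − 26.3) to 14.4 points (62.9 − 48.5). The simulation standard error of one power figure is at most √(0.25/1500) = 1.3 points, so the smallest gains are indistinguishable from none.
- Logistic regression with stratum alone differed from the chi-square by −0.8 to +0.4 points. The gain comes from enrolment temperature.
- Linear regression wins clearly in the first table and loses in the second. In that table's first row, only about 30% × (30% − 20%) = 3% of patients have a changed temperature, so the mean barely moves.
- With no treatment effect, the chi-square rejected in 5.5% of runs, against a standard error of √(0.05 × 0.95/1500) = 0.6 points. This is consistent with 5%.

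**The case against.** The strongest reply is that an unadjusted comparison of randomised arms is valid, and that this is half of one added secondary objective in a pilot. Protocol 8.4 says power did not set the sample size, Protocol 8.1 asks for caution with p-values, and fever is not among the go/no-go criteria. All of that stands and keeps the point minor. It does not explain why 7.6 gives no estimate when Protocol 8.1 asks for estimates.

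A reader might go further and infer any of the following, which the documents do not support.

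- **That the planned test throws away most of the information.** Step 1 shows this under a general temperature shift, but the documents give no fever prevalence, SD or effect. If the regimen only clears fevers, the yes/no outcome is the better one.
- **That week-2 temperature should replace fever resolution.** For the same reason, a continuous analysis cannot be assumed superior, and objective 6 names resolution.
- **That omitting the stratum is an error.** It costs almost no power, and the type I error holds. It is a matter of consistency and interpretation.
- **That the test definitely includes afebrile patients.** SAP 7.6 is silent, and resolution can be read as applying only to those febrile at enrolment. The defect is the silence.

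One further caution stands. If 7.6 is read as febrile patients only and the regimen acts only on clearance, that chi-square beats adjusted logistic regression in all patients by 2.0 to 7.9 points. Under a general shift it is 8.4 points (18.1 v 26.5) to 15.7 points (47.2 v 62.9) worse. The restricted test is therefore not a safe main analysis either.

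**Conclusion.** The point holds in a limited form. SAP 7.6 plans a valid but somewhat inefficient test. It reports no effect size, does not use enrolment temperature or stratum although both are recorded in both arms, and leaves the denominator open. The missing denominator and estimate can be read directly from the SAP and need no assumption.

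The efficiency loss is conditional. In the settings examined, adjusting the yes/no analysis for enrolment temperature and stratum gained between nothing distinguishable and about 14 points of power over the all-patient chi-square. The gain grows with the correlation between the two temperatures. Whether a continuous analysis would add more depends on how the regimen acts, which the documents do not say. No decision in the trial rests on this comparison.

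**What to change.** In SAP 7.6:

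1. **Main fever analysis.** Define fever for analysis as 38 °C or more, the cut-off already in the protocol. Analyse fever at week 2 in all patients by logistic regression on arm, enrolment temperature, new/retreatment stratum and hospital. Report the odds ratio with its 95% CI.
2. **Resolution proportion.** Report the proportion resolved, by arm, among patients febrile at enrolment.
3. **Supportive analysis.** Analyse week-2 temperature by linear regression with the same covariates and give the mean difference with its 95% CI. State that it supports the main analysis and does not replace it, so that the choice cannot follow the results.

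The cost is a few lines of SAP text, with no new data. The resolution proportion has a smaller denominator. If week-2 fever is rare, the model may be sparse: at an assumed 5% of 1000 patients there are 50 events. SAP section 6 already allows a reduced model when events are few. Section 7.6 should say in advance which terms are dropped, and enrolment temperature should be kept.

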### **2.3. Study hypothesis**

This study is a pilot study to estimate the differences in the incidences in adverse treatment outcomes and excess toxicity.

